4.10.2.6 Supplementary Analysis of Primary Objective

The treatment policy estimand is specified through the following definitions of population, variable, treatment condition, ICEs, and population-level summary:

Target population:	Defined by the inclusion/exclusion criteria.
Variable:	Change in log-transformed UACR from baseline to Week 12.
Treatment condition:	Zibotentan 1.5 mg combined with dapagliflozin 10 mg versus dapagliflozin 10 mg.
Intercurrent events:	Death, premature discontinuation from study treatment, or use of prohibited medication (Handled by the treatment policy strategy i.e. UACR data after the event will be included if collected. Deaths are expected to be relatively few and will be handled in the context of missing data).
Population-level summary:	Difference in least squares mean change in log-transformed UACR from baseline to Week 12 between zibotentan 1.5 mg combined with dapagliflozin 10 mg and dapagliflozin 10 mg.

The primary analysis in Section 4.10.2.2, excluding the sensitivity and subgroup analyses, will be replicated for the treatment policy estimand, with the exceptions that the analyses will be performed on the All Randomised Set and that step 1 in the MI (Section 4.10.2.3) will not exclude any UACR values from after an ICE.

4.10.2.7 Analysis of Secondary UACR Objectives

Comparison of zibotentan 0.25 mg and dapagliflozin 10 mg combined to dapagliflozin monotherapy (Secondary Objective Related to Primary Objective)

The geometric mean ratio of UACR for the zibotentan 0.25 mg combined with 10 mg dapagliflozin versus 10 mg dapagliflozin alone from baseline to Week 12 will be assessed. The MMRM model as described in Section 4.10.2.2 will be used to extract the results.

The results of the model parameters (estimates, p-values and 90% CIs) will be presented. Analyses and definitions described in Section 4.10.2.1, 4.10.2.2, 4.10.2.3, 4.10.2.4, 4.10.2.5 and 4.10.2.6 will be followed with the treatment arm adjusted as appropriate.

Dose-response Relationship Secondary Objective

The dose-response relationship between different doses of zibotentan/a fixed dose of dapagliflozin and UACR reduction will be characterised by assessing the UACR reduction analysed in the primary objective and the secondary objective related to the primary objective.

In order to select the dose for future studies, a more comprehensive PK analysis, including additional dose and exposure response models and modelling of safety events, will be performed by the AstraZeneca PK team based on subject level data. This will only be done where there is sufficient data that allows the AstraZeneca PK team to perform the modelling.

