4.3 Justification for Dose

Zibotentan

Zibotentan doses of 0.25, 1.5, and 5 mg (hereafter referred to as low, intermediate, and high dose, respectively) were initially selected to characterise the dose-UACR response relationship for zibotentan. Predictions were made using an exposure-UACR response model of clinical data from other ETA receptor antagonists, taking into account differences in PK and potency between the different compounds. Based on this model, 5 mg zibotentan was predicted to achieve a maximal UACR response. In participants with severe renal impairment, a dose of 5 mg will result in plasma exposure similar to that of 10 mg in subjects with normal renal function. Since 10 mg was associated with an increased fluid retention risk in earlier clinical studies, 5 mg was initially selected to be the highest dose used in this study involving a participant population with renal impairment. Based on the rate of fluid retention observed in an ad hoc safety interim analysis, randomisation to 5 mg zibotentan (both monotherapy and in combination with dapagliflozin) has been discontinued. The zibotentan 1.5 mg dose is predicted to cause less fluid retention than 5 mg, while at the same time producing meaningful UACR response, according to the model predictions. The zibotentan 0.25 mg dose was selected to be a minimally clinically relevant dose because it is predicted to produce a 20% or less reduction in UACR in addition to that with dapagliflozin.

Dapagliflozin

Dapagliflozin 10 mg is the approved dose for T2DM, CKD, and HF. 10 mg is the dose tested in DAPA-CKD for patients with CKD and an eGFR > 25 mL/min/1.73m² (NCT03036150).

Based on available preclinical and clinical data, the risk for metabolic drug-drug interactions between zibotentan and dapagliflozin is regarded as low.

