9.4.2.2 Secondary Endpoints

The change in UACR for zibotentan 0.25 mg combined with dapagliflozin 10 mg versus dapagliflozin 10 mg monotherapy from baseline (Visit 2) to Week 12 (Visit 7) will be assessed. A MMRM model similar to that described for the primary endpoint will be fitted.

The dose-response relationship between different doses of zibotentan/a fixed dose of dapagliflozin and UACR reduction will be characterised by assessing the UACR reduction analysed in primary and first secondary objective.

The change from baseline (Visit 2) to Week 12 (Visit 7) in office systolic and diastolic BP will be assessed for doses of zibotentan combined with dapagliflozin 10 mg compared to dapagliflozin 10 mg monotherapy.

The effect of different doses of zibotentan and dapagliflozin in combination on eGFR will be determined from the change in eGFR from baseline to Week 1, Week 12, and Week 14, and from Week 1 to Week 12.

These secondary variables of BP and eGFR will be analysed using ANCOVA, adjusting for stratification factors, treatment arm, and baseline. The FAS will be used for these analyses. More details will be provided in the SAP.

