2.2 Secondary Objectives

Secondary Objectives ^a	Endpoints

 • To evaluate the effect of zibotentan 0.25 mg/dapagliflozin 10 mg versus dapagliflozin 10 mg monotherapy on UACR. 	
 • Change in log-transformed UACR from baseline to Week 12.

 • To determine the change in office systolic and diastolic BP for doses of zibotentan combined with dapagliflozin 10 mg versus dapagliflozin 10 mg monotherapy. 	
 • Change in BP from baseline (Visit 2) to Week 12.

 • To characterise the dose-response relationship (relationship between different doses of zibotentan/a fixed dose of dapagliflozin and UACR reduction). 	
 • Change in log-transformed UACR from baseline to Week 12.

 • To determine the effect of different doses of zibotentan and dapagliflozin 10 mg in combination versus dapagliflozin 10 mg monotherapy on eGFR. 	
 • Change in eGFR from baseline to Week 1. • Change in eGFR from baseline to Week 12. • Change in eGFR from baseline to Week 14. • Change in eGFR from Week 1 to Week 12.

Abbreviations: BP = blood pressure; eGFR = estimated glomerular filtration rate; UACR = urinary albumin to creatinine ratio

^a The estimand for the secondary objectives is defined with the same approach as for the primary objective.

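### The dose-response objective is answered only from two comparisons with dapagliflozin; no 1.5 mg versus 0.25 mg estimate, with its uncertainty, is planned

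*SAP*

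**What the plan says.** The secondary objective in SAP 2.2 concerns the "relationship between different doses of zibotentan/a fixed dose of dapagliflozin and UACR reduction". SAP 4.10.1.1 also states that the trial is designed to assess dose-response, alongside testing superiority.

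For the analysis, SAP 4.10.2.7 says that the relationship "will be characterised by assessing the UACR reduction analysed in the primary objective and the secondary objective related to the primary objective". Protocol 9.4.2.2 agrees: it is to be "characterised by assessing the UACR reduction analysed in primary and first secondary objective". The primary comparison is 1.5 mg versus dapagliflozin and the related secondary comparison is 0.25 mg versus dapagliflozin. For the latter, "The results of the model parameters (estimates, p-values and 90% CIs) will be presented". Neither document specifies a 1.5 mg versus 0.25 mg contrast or a trend test, or says how assessing the two results leads to a conclusion.

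SAP 4.10.2.7 adds, for selecting the dose for future studies, "a more comprehensive PK analysis, including additional dose and exposure response models and modelling of safety events" by the sponsor's PK team, with the condition "This will only be done where there is sufficient data". SAP 4.14 places the dose-response models outside the CSR.

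On expected effects, Protocol 4.3 chose 0.25 mg as a minimally relevant dose because "it is predicted to produce a 20% or less reduction in UACR in addition to that with dapagliflozin".

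**The concern.** With zibotentan at 0, 0.25 and 1.5 mg on fixed dapagliflozin, a dose-response statement has two parts: whether each dose differs from zero, and what happens between 0.25 and 1.5 mg. The planned comparisons answer the first part. For the second, the CSR would give neither an estimate nor an interval.

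Readers will still look at the two results side by side. The natural shortcut is to see that one dose is significant and the other is not, and conclude that the doses differ. Neither test has equality of the two doses as its null. The 0.25 mg arm is half the size of the others, so at the same true effect its test is weaker. The two comparisons also share the dapagliflozin arm, so their intervals cannot be combined as if they were independent.

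At stake is how clearly the trial describes the efficacy difference between its two remaining zibotentan doses. This is a point about estimation and takes no position on which dose is right.

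**Working it through.** **Inputs from the documents**
- One-sided alpha of 0.05; 150 evaluable in the 1.5 mg arm and in the dapagliflozin arm (SAP 4.14, Protocol 9.2).
- 0.25 mg arm: 75 evaluable in SAP 4.14, 77 in Protocol 9.2.
- Drop-out of 10%; randomised 166, 166 and 83, total 415 (SAP 4.14).

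**Assumed, because redacted:** power of 50% to 99% for 1.5 mg versus dapagliflozin; SD of log UACR change of 0.7 to 1.0 where an SD is needed.

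**Reproducing the plan's own figure.** 150/0.9 = 166.7 against 166 stated, and 75/0.9 = 83.3 against 83 stated; 166 + 166 + 83 = 415. The protocol's 77 would give 77/0.9 = 85.6, so 75 is used below. The stated power cannot be reproduced.

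**Set-up, in SD units**
- SE of 1.5 mg versus dapagliflozin: sqrt(1/150 + 1/150) = 0.115.
- SE of 0.25 mg versus dapagliflozin: sqrt(1/75 + 1/150) = 0.141.
- Correlation through the shared control: (1/150)/(0.1155 × 0.1414) = 0.408.
- True effect giving power p for 1.5 mg: d = (1.645 + z_p) × 0.1155. At 80%: (1.645 + 0.842) × 0.1155 = 0.287.
- With the same d, power for 0.25 mg at that point: Φ(0.287/0.1414 − 1.645) = 0.650.

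**If both doses act equally** (bivariate normal; simulation of 1,000,000 trials at 80%, 90% and 95% power agrees):

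| Power, 1.5 mg | d | Power, 0.25 mg | Both significant | Only 1.5 mg | Only 0.25 mg |
|---|---|---|---|---|---|
| 50% | 0.190 | 0.381 | 0.254 | 0.246 | 0.127 |
| 60% | 0.219 | 0.462 | 0.341 | 0.259 | 0.121 |
| 80% | 0.287 | 0.650 | 0.566 | 0.234 | 0.084 |
| 90% | 0.338 | 0.772 | 0.720 | 0.180 | 0.051 |
| 95% | 0.380 | 0.851 | 0.822 | 0.128 | 0.029 |
| 99% | 0.459 | 0.945 | 0.938 | 0.052 | 0.007 |

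The only-1.5-mg pattern peaks at 0.260, near 64% power. With 77 in the 0.25 mg arm it is 0.255, 0.229 and 0.174 at 60%, 80% and 90% power. As examples, a shared 20% reduction gives 20% at SD 0.7 and 26% at SD 1.0.

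**Share due to unequal arms.** With 150 in every arm and the same power, the pattern still occurs in 0.161, 0.113 and 0.068 of trials at 60%, 80% and 90%. Halving the 0.25 mg arm adds 0.259 − 0.161 = 0.098, 0.234 − 0.113 = 0.121 and 0.180 − 0.068 = 0.112, or about 10 to 12 points. It also makes the error lopsided: 23% against 8% for the reverse pattern at 80% power.

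**The direct contrast**
- SE = SD × sqrt(1/150 + 1/75) = 0.141 × SD.
- Combining the two dapagliflozin comparisons as if independent gives sqrt(2/150 + 3/150) = 0.183 × SD, which is 0.183/0.141 − 1 = 29% too large.
- 90% CI factor, exp(1.645 × 0.1414 × SD): 1.18 at SD 0.7 and 1.26 at SD 1.0.
- Between-dose reduction detectable with 80% power, 1 − exp(−(1.645 + 0.842) × 0.1414 × SD): 22% at SD 0.7 and 30% at SD 1.0.
- Tested one-sided at 5%, it would wrongly favour 1.5 mg in 5% of trials when the doses act equally.

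**The case against.** The plan is not a pair of bare tests. Estimates and 90% CIs accompany the p-values, and SAP 4.10.2.2, carried over by 4.10.2.7, also gives each arm's geometric mean with a 90% CI. From these a careful reader could approximate the between-dose ratio: sqrt(1/150 + 1/75) is just the two arm-level errors combined. No SAP rule reads dose-response from one significant and one non-significant result, so the pattern frequencies belong to a reading that the SAP neither sets nor rules out. All of this stands. It limits the point to a missing prespecified estimate, though it does not supply one.

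Zero is itself a dose level in both sample-size sections. If both doses reduced UACR equally, there would be a dose-response that rises from zero and then plateaus. A reader might infer that the CSR could report a dose-response that does not exist. The documents do not support that: what could be misread is the shape between 0.25 and 1.5 mg.

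Equal effects also depart from the premise in Protocol 4.3 that 0.25 mg is a minimally relevant dose. That stands, and the calculation is a what-if. If the doses do differ as expected, an estimate of how much and how precisely is still wanted.

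Finally, dose selection is assigned to the PK team's modelling, and Protocol 9.4.4.1 and SAP 4.12.1 plan summaries of dose relative to PD variables, including urine albumin and creatinine. But the modelling is conditional on sufficient data, its method is not stated, and SAP 4.14 puts the dose-response models outside the CSR. The PD summaries are presented by treatment arm, with no between-dose contrast specified.

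**Conclusion.** The point holds as a gap in estimation: the dose-response objective has no prespecified estimate, or uncertainty, for the difference between its two active doses.

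If a reader compared p-values and the doses acted equally, the misleading pattern would occur in roughly 5-26% of trials for 1.5 mg power between 99% and 50%. It is about 13% at 95% power and falls below 5% beyond 99%. This rests on 150/75/150 evaluable, one-sided 5% tests, a normal approximation and equal effects. Because planning power, effect and SD are redacted, no narrower range can be claimed for this trial.

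A reader might also infer that the 2:1:2 allocation creates the problem. It does not do so alone: equal arms of 150 still give the pattern in 7-16% of trials at 60-90% power. This is a cheap improvement to the plan. It does not put the primary analysis in doubt.

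**What to change.** Add to SAP 4.10.2.7 and Protocol 9.4.2.2:

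*The Week 12 geometric mean ratio of zibotentan 1.5 mg/dapagliflozin 10 mg versus zibotentan 0.25 mg/dapagliflozin 10 mg, with its 90% CI, will be estimated as a contrast from the MMRM in SAP Section 4.10.2.2. Statements about a difference between the two doses will rest on this contrast.*

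SAP 4.10.2.7 already takes the 0.25 mg result from that MMRM, while Protocol 9.4.2.2 speaks of fitting a similar model. The contrast needs all three arms in one fit, and the added text should say so.

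The cost is one extra contrast and one short addition to each document, with no new data. The downside is moderate power: 80% for a between-dose reduction of about 22-30% at assumed SD 0.7-1.0. For true add-on reductions of 30% and 10% at SD 0.85, power is 67%: (ln 0.9 − ln 0.7)/(0.85 × 0.1414) = 2.09, and Φ(2.09 − 1.645) = 0.67. The result may therefore be inconclusive, in which case the interval would show that.

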4.10.3 Analysis of Secondary Objectives Other Than UACR

The secondary efficacy variables will be based on a similar estimand to the primary estimand for the primary objective in Section 4.10.2.1, with the variable and population-level summary updated to be relevant to the secondary efficacy variable specified.

Office systolic and diastolic BP

The change from baseline to Week 12 in office systolic and diastolic BP will be assessed for doses of zibotentan combined with dapagliflozin 10 mg compared to dapagliflozin 10 mg monotherapy. This will be analysed using the MMRM method specified in Section 4.10.2.2, adjusting for the same variables, though with baseline BP replacing baseline log(UACR). The FAS will be used for this analysis and BP will be evaluated on the original scale.

The results of each MMRM will be presented by treatment arm. A summary of change from baseline of office systolic and diastolic BP results will be presented by treatment arm and a by-participant listing of office systolic and diastolic BP results at each visit will be provided. Plots of the mean office systolic and diastolic BP over time up to follow-up visit will be presented.

As a sensitivity analysis, a MMRM will be performed for office systolic and diastolic BP up to Week 12, analysed on the PPS, similarly to that described above.

eGFR

The effect of different doses of zibotentan and dapagliflozin in combination compared to dapagliflozin 10 mg monotherapy on eGFR will be determined from the change in eGFR from baseline to Week 1, from baseline to Week 12, from baseline to Week 14 and from Week 1 to Week 12. Change from baseline to Week 1, baseline to Week 12, baseline to Week 14 and Week 1 to Week 12 will be analysed using the MMRM methodology specified in Section 4.10.2.2. Change from baseline to Week 1, change from baseline to Week 3, change from baseline to Week 6, change from baseline to Week 9, change from baseline to Week 12 and change from baseline to Week 14 will be included in the model, adjusting for the fixed categorical effects of CSP version (Amendment 2 versus pre-Amendment 2), diabetes (DKD versus non-DM CKD), treatment visit, and treatment-by-visit interaction, plus the continuous covariates of baseline eGFR and baseline eGFR-by-visit interaction. The FAS will be used for these analyses and eGFR will be evaluated on the original scale.

The results of each MMRM will be presented by treatment arm. A summary of change from baseline of eGFR results will be presented by treatment arm and a by-participant listing of eGFR results at each visit will be provided. A plot of the least squares means by treatment arm over time will be presented.

As a sensitivity analysis, a MMRM will be performed for eGFR from baseline to Week 1, from baseline to Week 12, from baseline to Week 14 and from Week 1 to Week 12, analysed on the PPS, similarly to that described above.

A visual inspection of the plot of the least squares means, mentioned above, will be used to examine the eGFR slope from baseline to Week 12.

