Day	-28	1	8	22	43	64	84	98		
Day Visit Window	+7/ -14		±1	±2	±2	±2	±2	±3		
Spot urine from first morning void over 3 consecutive days: albumin, creatinine (central laboratory)		X		X	X		X	X	Spot urine from first morning void over 3 consecutive days, ideally on day of clinic visit and preceding 2 days, collected at home in provided vials. Analysis will be done in all 3 samples at central laboratory and averaged.	Section 8.1.1
Spot urine from first morning void: Na ⁺ , K ⁺ , uric acid, urea, glucose, creatinine, osmolality, and cortisol (central laboratory)		X		X	X		X	X	Spot urine from first morning void, only from the third day sample (day of clinic visit), collected at home in provided vial. Analysis will be done at central laboratory.	Sections 8.5.3 and 8.5.3.1
Body weight	X	X	X	X	X		X	X	Body weight must be taken and reviewed before treatment at each dosing visit.	Sections 8.2.2 and 5.1
Echocardiography	X						X		Screening and Week 12 only. ECHO will be performed locally and sent to central reader. Results need to be available before randomisation.	Section 8.1.3.3
Bioimpedance spectroscopy		X	X	X	X		X	X		Section 8.1.3.2
Home-based monitoring										
Daily digital body weight measurement		Daily home measurement using a digital device from randomisation to end of follow up.							Home body weight measurements should start 2 days before randomisation (same as for spot urine).	Section 8.1.3 and Section 8.2.1

Procedure	Screening	Interventional period							Follow-up	Notes	Details in CSP Section/Appendix
		1	2	3	4	5	6	7 (ED)			
Visit	1	2	3	4	5	6	7 (ED)	8			
Week	-4	0	1	3	6	9	12	14			
Day	-28	1	8	22	43	64	84	98			
Day Visit Window	+7/ -14		±1	±2	±2	±2	±2	±3			
Pharmacodynamics											
Plasma/serum K ⁺ , Na ⁺ , uric acid, BUN, fasting plasma glucose, cystatin C, haematocrit, haemoglobin, ET-1, ELDP, CT-proET-1, copeptin, NT-proBNP, and BNP (central laboratory)	X	X	X	X	X	X	X	X	Results for central BNP testing must be reviewed within 24 hours of receipt by the investigator.	Section 8.2.4 and 8.5.3.1	
BNP or NT-proBNP (local laboratory)	X								Results need to be available before randomisation.	Section 8.2.4	
Safety assessments											
Adverse event review	X SAEs only	X	X	X	X	X	X	X		Section 8.3	
Vital signs (blood pressure, pulse, respiratory rate)	X	X	X	X	X	X	X	X	Vital signs at Visit 2 need to be performed and the results reviewed before randomisation in IWRS.	Section 8.2.2 and 8.1.2.1	

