7 DISCONTINUATION OF STUDY INTERVENTION AND PARTICIPANT DISCONTINUATION/WITHDRAWAL

7.1 Discontinuation of Study Intervention

It may be necessary for a participant to permanently discontinue (definitive discontinuation) study intervention.

An individual participant **may be** discontinued from study intervention in the following situations:

- Participant decision. The participant is at any time free to discontinue treatment, without prejudice to further treatment.
- An AE that, in the opinion of the investigator or AstraZeneca, warrants discontinuation from further dosing.
- Severe non-compliance with the CSP.
- Safety reasons as judged by the investigator and/or sponsor where continued treatment may put participant at undue risk.

An individual participant **will be** discontinued from study intervention in the following situations:

- If BNP is increased > 100% from baseline AND is greater than 200 pg/mL; or if BNP is increased > 100% from baseline AND is greater than 400 pg/mL in a participant with atrial fibrillation.
- If the participant or male participant's partner becomes pregnant during the course of the study, investigational products should be discontinued immediately, and an AZ representative notified.
- Diabetic ketoacidosis: DKA including euglycemic DKA have been reported with use of dapagliflozin. Consider temporary interrupting study treatment if DKA is suspected. The participant should be promptly evaluated. If diabetic ketoacidosis is confirmed, investigational product(s) should be discontinued permanently. If diabetic ketoacidosis is not confirmed, restart of study intervention should be considered (see Section 7.1.1 for details).
- Symptomatic hypotension (defined as systolic BP < 90 mmHg OR diastolic BP < 60 mmHg with symptoms).
- eGFR reduction: investigational study products must be discontinued in case of confirmed eGFR reduction from baseline >50% and/or any confirmed decrease below 15 mL/min/1.73m².

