4.10.2 Analyses of UACR Objectives

4.10.2.1 Primary Estimand for Primary Objective

The primary estimand is a hypothetical estimand such that the treatment effect is quantified in the optimal situation where any potential confounder is minimised. The analysis will be performed on the FAS. The endpoint being assessed is the change in log-transformed UACR from baseline to Week 12. Participants will be included in the analysis if they have a non-missing baseline and at least one non-missing post-treatment visit UACR measurement.

For the intercurrent events (ICEs), if a participant dies, prematurely discontinues study treatment, or uses prohibited medication, the UACR data are treated as missing after the event and no imputation will be performed. The summary measure being evaluated is the geometric mean reduction of UACR from baseline to Week 12.

The estimand is specified through the following definitions of population, variable, treatment condition, ICEs, and population-level summary:

Target population:	Defined by the inclusion/exclusion criteria.
Variable:	Change in log-transformed UACR from baseline to Week 12.
Treatment condition:	Zibotentan 1.5 mg combined with dapagliflozin 10 mg versus dapagliflozin 10 mg.
Intercurrent events:	Death, premature discontinuation from study treatment, or use of prohibited medication (Handled by hypothetical strategy i.e. UACR data are treated as missing after the event. Deaths are expected to be relatively few and will be handled in the context of missing data).
Population-level summary:	Difference in least squares mean change in log-transformed UACR from baseline to Week 12 between zibotentan 1.5 mg combined with dapagliflozin 10 mg and dapagliflozin 10 mg.

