4.10.2.2 Primary Analysis of Primary Objective

The primary efficacy endpoint for this study is the change in log-transformed UACR from baseline to Week 12. As UACR is assumed to follow a log-normal distribution, it will be log-transformed for statistical analysis purposes. The mean log changes in UACR at Week 12 (\hat{Y}_1, \hat{Y}_2) for zibotentan 1.5 mg combined with dapagliflozin 10 mg and dapagliflozin 10 mg alone will be estimated using a mixed model repeated measures [MMRM] method (Weeks 3, 6, 9, and 12). The least squares means will be back transformed to give the geometric mean change from baseline to Week 12. The geometric means will be converted to percentage mean change for Week 12 from baseline on the original scale using the following formula:

$$(\text{GeoMean}(UACR_{\text{Week12-Baseline}}) - 1) \times 100$$

The change in UACR from baseline to Week 12 for zibotentan 1.5 mg combined with dapagliflozin 10 mg compared to the dapagliflozin 10 mg monotherapy arm will be presented as a geometric mean ratio. The analysis model will include the fixed categorical effects of CSP version (Amendment 2

versus pre-Amendment 2), diabetes (DKD versus non-DM CKD), treatment, visit, and treatment-by-visit interaction, plus baseline eGFR strata (≤ 45 versus > 45 mL/min/1.73 m²), log(UACR) and baseline log(UACR)-by-visit interaction. An unstructured covariance structure will be used for the within-participant errors. The denominator degrees of freedom will be estimated using the Kenward-Roger approximation. If the MMRM model does not converge using an unstructured covariance structure, the Toeplitz, first-order autoregressive or compound symmetric covariance structure will be used. If that does not resolve the convergence issues, the analysis will be altered to use an analysis of covariance (ANCOVA) with a missing at random (MAR) multiple imputation (MI) method implemented (Section 4.10.2.3).

The geometric means, along with the conversion to percentage, for change from baseline to Week 12 from the model, and the 90% confidence intervals will be presented. The geometric mean ratio, which is the back-transformed least squares mean difference in change from baseline to Week 12 between two treatment arms, will be converted to adjusted percentage mean change between treatment arms as follows:

$$[(\text{Geometric Mean Ratio} - 1) \times 100]$$

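### Read literally, the SAP fits the blood-pressure MMRM from Week 3 onward, so the Week 1 BP already collected is left out of the modelled Week 12 contrast

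*SAP*

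**What the plan says.** The BP paragraph of SAP 4.10.3 defines its model by cross-reference: "This will be analysed using the MMRM method specified in Section 4.10.2.2, adjusting for the same variables". It then makes two changes. One is to the covariate, "though with baseline BP replacing baseline log(UACR"; the other is that BP stays on its original scale. It does not mention visits.

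The model referred to, in SAP 4.10.2.2, does name its visits: "mixed model repeated measures [MMRM] method (Weeks 3, 6, 9, and 12".

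The row "Vital signs (blood pressure, pulse, respiratory rate" in the Schedule of Activities (Protocol 1.3) is marked at every visit, including Visit 3 at Week 1. The UACR row has no Week 1 sample, which explains why the UACR list starts at Week 3.

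The eGFR paragraph of SAP 4.10.3 also points to 4.10.2.2 but writes out its own visits, beginning "Change from baseline to Week 1, change from baseline to Week 3, change from baseline to Week 6" and running to Week 14.

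On missing data, SAP 4.10.3 says "The secondary efficacy variables will be based on a similar estimand to the primary estimand". Under the primary estimand, once treatment is stopped early, "the UACR data are treated as missing after the event and no imputation will be performed".

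Protocol 7.1 lists among the reasons for which treatment will be stopped: "Symptomatic hypotension (defined as systolic BP < 90 mmHg OR diastolic BP < 60 mmHg with symptoms".

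**The concern.** A likelihood-based MMRM gives a valid Week 12 contrast under missing-at-random when the observed values that predict dropout are in the model. Here one of the mandatory stopping criteria is defined by BP itself, and Week 1 is the only scheduled on-treatment BP before Week 3. If that value is left out, stopping between Weeks 1 and 3 has to be ignorable given baseline and the other covariates alone. That is a stronger assumption than the data require.

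If low early BP leads to stopping, and this happens more often in the zibotentan arms, the people removed are those with the larger BP falls. The modelled Week 12 reduction then comes out too small. BP is a secondary endpoint, and Protocol 4.2 names hypotension as a special safety focus.

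**Working it through.** **Step 1: who is lost.** SAP Table 5 maps Days 2 to 15 to Week 1 and Days 16 to 32 to Week 3. Values after treatment stops are set to missing. A participant with an on-treatment BP on Days 2 to 15 and none from Day 16 therefore has no response at Weeks 3, 6, 9 or 12. An unscheduled on-treatment BP from Day 16 would keep the participant in, because unscheduled visits are mapped to the windows.

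**Step 2: whether another planned BP model recovers them.**
- The BP sensitivity model uses the per-protocol set, which requires at least 6 weeks of treatment (SAP Table 6), so it does not.
- The treatment-policy analysis (SAP 4.10.2.6) covers the primary UACR comparison and is extended in 4.10.2.7 only to the other UACR comparison. Visits continue after stopping (Protocol 7.1), but no planned BP model uses those later values.

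**Step 3: arm size.** SAP 4.14 plans 150 evaluable participants per main arm with 10% drop-out: 150 / 0.90 = 166.7, against the stated 166. The plan thus allows for 166 - 150 = 16 losses per main arm for all reasons, which is an outer bound on the group at issue.

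**Step 4: size of the effect.** From the documents: 166 per arm, and a BP reduction of about 5 mmHg (Protocol Table 2, hypotension row), used here as the true between-arm difference at every visit. Assumed, because the documents give no figure:
- SD of change 12 mmHg with between-visit correlation 0.4, or SD 16 mmHg with correlation 0.6;
- everyone whose Week 1 change falls below a fixed cut-off stops before Week 3. The same cut-off applies in both arms and is set so that a given share of the combination arm stops;
- no baseline covariate in this version.

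Each setting was simulated 3,000 times, with maximum likelihood for monotone missing data, with and without Week 1. The Monte Carlo error of each mean is about 0.02 to 0.03 mmHg (for example 1.33 / √3000 = 0.024).

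| Combination arm stopping early | Participants of 166 | Mean estimate without Week 1 (mmHg) | Shortfall from 5 mmHg | Mean estimate with Week 1 (mmHg) |
|---|---|---|---|---|
| 1% | 1.7 | -4.92 to -4.83 | 0.08 to 0.17 | -5.01 to -4.97 |
| 2% | 3.3 | -4.87 to -4.75 | 0.13 to 0.25 | -5.02 to -5.00 |
| 5% | 8.3 | -4.69 to -4.59 | 0.31 to 0.41 | -5.05 to -4.97 |
| 10% | 16.6 | -4.52 to -4.27 | 0.48 to 0.73 | -5.02 to -4.99 |

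The 10% row uses up the whole drop-out allowance and is an extreme case. Precision hardly changes: at 5% stopping, the SD of the estimate is 1.34 without and 1.36 with Week 1 (first setting), and 1.77 and 1.81 (second setting).

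**Step 5: with baseline adjustment.** The planned model adjusts for baseline BP, so a large-sample check added it. Assumptions: baseline SD 15, SD of change 13, baseline-change correlation -0.35, Week 1 to Week 12 correlation 0.4 to 0.6, and stopping in the combination arm only, driven by the Week 1 BP level plus noise of SD 15. With 2% to 4% stopping, the estimate without Week 1 is -4.90 to -4.68, a shortfall of 0.10 to 0.32 mmHg.

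**Step 6: scale.** At SD 13 and 150 per arm, the standard error of an unadjusted difference is 13 × √(2/150) = 1.5 mmHg. The shortfall at 1% to 5% stopping is well inside that.

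**The case against.** The strongest reply is that the SAP never says Week 1 is excluded. The Week 3 to 12 list sits in a sentence about UACR, the BP text imports a method and its covariates, and the per-protocol BP sentence speaks only of modelling up to Week 12. A programmer could fairly include Week 1. The eGFR list is weak evidence of intent, since eGFR has Week 1 and Week 14 endpoints and needs those visits, while the BP endpoint is Week 12 only. This stands to the extent that the point concerns the literal reading. It does not remove the need for a change, because two programmers could fit different models from the same text.

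Second, no document supports a particular rate of early, BP-driven stopping. Protocol Table 2 says that hypotension with zibotentan has usually been without symptoms, while the stopping criterion requires symptoms. This stands. In addition, the full recovery with Week 1 in the model follows from letting stopping depend on Week 1 BP. If symptoms arise after Visit 3, adding Week 1 need not remove all of the bias.

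Third, the protocol's ANCOVA (9.4.2.2), if fitted without imputation, would lose everyone without a Week 12 value, so the SAP model is no worse in this respect. That is correct, but it is no reason to leave out available data.

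A reader might also infer that early oedema strengthens the case, since Protocol Table 2 says it tends to appear within a month. The documents do not link oedema to a fall in BP, so it does not show that early stoppers have low BP. Nor is the hypotension signal hidden: SAP 4.10.3 and 4.11.5 provide by-visit BP summaries, plots, listings and counts of notable changes, Week 1 included, and these participants stay in the Full Analysis Set.

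**Conclusion.** The point holds as a low-cost improvement to the model as written. On a literal reading, the BP MMRM omits a scheduled on-treatment measurement, and anyone whose only on-treatment BP falls on Days 2 to 15 contributes nothing to the modelled Week 12 contrast.

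If early stops are driven by low Week 1 BP, the reduction is understated by probably a few tenths of a mmHg: about 0.1 to 0.4 of an assumed 5 mmHg at 1% to 5% early stopping. If such stops are rare, the effect is negligible. These figures depend on the assumed SD, correlation, stopping rate and selection mechanism. The direction, toward a smaller BP effect, applies to stops caused by low BP and not necessarily to other early stops.

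A reader might infer a bias of 10% or more of the effect. The calculation without baseline adjustment reaches that size only near the extreme 10% stopping rate, where 0.48 to 0.73 of 5 mmHg is about 10% to 15%. The documents give no basis for expecting that rate.

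**What to change.** In the BP paragraph of SAP 4.10.3, state that the MMRM response vector is the change from baseline at Weeks 1, 3, 6, 9 and 12, with the treatment contrast taken at Week 12. Use the same visits in the per-protocol sensitivity model. If the ANCOVA with multiple imputation is needed as the fallback, include Week 1 BP in the imputation model.

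The cost is about one sentence and no new data. The unstructured covariance matrix grows from four visits to five, against six already planned for eGFR, and the simulation showed almost no loss of precision.
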